After the appointment, PrEP medication will be delivered to Prevention Point in weekly packets. Each participant will be assigned a small locked locker and study staff will place a week's worth of medication in the locker every Monday. Participants can then pick up the medication when it's convenient for them and study staff can keep track of whether medication has been picked up. This information will be provided to the PrEP counselors so they can follow up with the participant if medication has not been picked up.

It is expected that participants will meet with their PrEP counselor at least four times during the intervention. For the “Enhanced” group, the PrEP counselor will reach out, emphasize study messages, and set up at least monthly appointments after the initial appointment. For the “Basic” group, PrEP counselors will meet with women at initial appointment and for the next three weeks. They will then be available as needed and will meet with participants when they request, but they will not actively reach out to participants which is how PrEP counseling is currently taking place. For an example of how targeted messages would be delivered in the “Enhanced” group, see table 2.

Table 2. Targeted messages for “Enhanced” group

Potential Construct from Vector Modeling	In-clinic PrEP Counseling	Written/Visual Materials	Text Message
Staying HIV- is worth taking a daily medication for.	HIV is no joke. The best way to stay HIV- is to be on PrEP. It's just one pill a day and it can significantly lower your risk of getting it.	We know you have a lot going on but if you set up a time to take the pill every day, it will get easier. We can help you think about how to add this to your day. Ask us!	Remember, it's only 1 pill a day. U can do it and we can help!
Worry about being able to take medication every day	It can be a pain to take medication every day but it's worth the effort because you can be sure that you stay free from HIV.	You may not want to take medication every day because of the time and effort it takes. But it is worth it. It can give you the peace of mind to know that you are HIV free.	Get peace of mind! Take your medication every day. Call XXX-XXX-XXXX if you have ??

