Mosio will have no identifying information other than a participant’s phone number. Mosio will collect user data on the number of participants who open the text messages and will also resend text messages if they remain unopened for more than two days to assess feasibility. In addition, participants will be provided the opportunity to engage with study personnel if they have questions. A phone number will be provided in every text and study personnel will be available to take participant’s phone calls and answer their text messages. All messages/calls are sent to the study coordinator’s email and we will provide language that indicates that if questions are after business hours of 9 am to 5 pm we will answer the question the next morning. There will also be an opportunity to provide feedback. At mid-intervention participants will be asked to text back an answer to an adherence question. This provides an opportunity for participants to be actively engaged and to assess feasibility and acceptability. We will receive weekly reports from Mosio on which participants have opened text messages to assess feasibility.

At the end of the first month, all participants will also receive a text asking about their adherence to PrEP. They will respond with a 1 or 0 to indicate they have or have not taken PrEP the previous day. To help alleviate any problems with running out of cell phone minutes, every participant will receive a \$25 gift card to help pay for minutes needed. If they lose or have their cell phone stolen, we will assist them in getting a new one through the current services at PPP.

PPP has a current service that provided assistance to clients and we will work with them to help the study participant.

At the end of the first month we will also contact participants about completing a quick assessment of adherence and acceptability of the intervention. This will be done in person at Prevention Point. Similarly, at the end of the three-month intervention study staff will contact participants about completing a post-test assessment. We will attempt to correspond assessments to be at a time when they are already at Prevention Point and ideally meeting with their PrEP counselor or there for other services.

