Participants will also continue to be monitored by the physician at Prevention Point. It is expected that a blood test or urine sample measuring PrEP levels and an HIV screening test would be done at the beginning, mid-point and the end of the intervention. It will also be done three months after the intervention is over. This will provide biomedical adherence data and ensure that participants have remained HIV negative.

After the intervention is over, all study participants may continue their PrEP prescription and have it administered out of the medical clinic at Prevention Point. In addition, PrEP counselors will remain available for participants should they have any further questions. Specialized counseling and text messages will no longer be provided. Three months after the intervention is over, we will contact participants to complete the last study assessment. This will be done at Prevention Point when the participant is there.

Instruments

There are five study assessments (See attachments). They include:

1. Eligibility Screener
2. Baseline Assessment
3. Mid-Intervention Assessment (in person and one question via text)
4. Post-Intervention Assessment
5. Three month follow-up Assessment

Analysis Plan

General - All data will be graphed and tabulated by treatment group for review of distributional properties and anomalous values prior to the main analyses. Continuous and normally distributed variables will be summarized with means and standard deviations. All parameter estimates will be bound by 95% confidence intervals and tests for differences in means and proportions will be deemed statistically significant $p < 0.05$. Post-hoc tests of significance will be based on adjustments for alpha to protect family-wise error rates at 5% using the method of Benjamini & Hochberg. For all analyses described in this study, we will use Statistical Analysis Software (SAS, version 9.4, Cary, N.C.).

Primary Outcome. The study's intent is to provide directional insight into the design of subsequent programmatic studies. As such, univariate group comparisons will be accomplished using an independent two-sample t-test for continuous measures (or non-parametric Wilcoxon

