Participation may contribute to increasing participants' initiation and adherence of PrEP, which will lower their HIV risk. Participation also may help participants consider how perceived stigma impacts their feelings about PrEP and help "normalize" the use of HIV prevention within the IDU community. The risks of discomfort or embarrassment discussing HIV and PrEP are reasonable in relation to the anticipated direct benefits to the subjects and the contribution subjects can make to society by reducing HIV stigma among WWIDs and encouraging HIV prevention efforts among their peers.

Privacy

As noted, all data will be coded to protect the confidentiality of participants. Only the Principal Investigator and the study coordinator will have access to the list of actual participant names and cell phone numbers. That list will be kept in a locked file (hardcopy only) in the office of [name]. The REDCap dataset with the coded data, with names removed, will be stored behind the firewall of Temple University. Medical information (adherence, HIV tests etc.) in medical charts will not be removed from Prevention Point. The study coordinator will access this through Prevention Point's electronic health record and note findings in the de-identified REDCap

database that will assign an ID number for each participant. Information will be entered into REDCap as coded data (i.e. adherence is coded 0 as no, 1 as yes). The PrEP counselors will know the names of the participants, but they will not have access to the REDCap database or participant medical records. The research assistant will only have access to de-identified data.

Compensation

Participants will receive up to a total of \$175 in gift cards. These incentives will be provided for different steps of the research study. Compensation will not be provided to those who drop out of the study or do not complete the step. Compensation will be broken down as follows:

- \$5 for conducting the eligibility screener and HIV test
- \$15 for completing the baseline test
- \$40 for meeting with the PrEP counselor (Up to four times, \$10 each time)
- \$15 for doctor visits (three times, \$5 each time)
- \$10 for completing one-month survey
- \$20 for completing three month survey
- \$50 for completing three month follow up survey
- \$20 for cell phone minutes

References

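### The stated preference for assessing women at counselor meetings can make survey timing, setting and completeness differ by arm, clearly at month three and slightly at month one

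*Combined protocol and SAP*

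**What the plan says.** Procedure Phase 3 has study staff contact participants at the end of month one and of month three for an in-person assessment. No distinction is made by arm. Staff will attempt to place these assessments "at a time when they are already at Prevention Point and ideally meeting with their PrEP counselor", or when they have come in for some other service.

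The same section sets the counseling schedule. In Enhanced, the counselor reaches out and will "set up at least monthly appointments after the initial appointment". In Basic, "PrEP counselors will meet with women at initial appointment and for the next three weeks"; after that, counselors are available on request, "but they will not actively reach out to participants which is how PrEP counseling is currently taking place". The Randomized Pilot text under Study Design is shorter: monthly counseling in the intervention arm, and counseling at the participant's request in the control arm.

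For the last assessment, three months after the intervention, staff again contact participants: "This will be done at Prevention Point when the participant is there". Specialized counseling has stopped by then.

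Adherence is the primary outcome, measured by self-report and by blood or urine sample. Self-efficacy, PrEP attitudes and decisional conflict are secondary and come from the surveys.

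**The concern.** An outcome assessment should be reached by the same route in both arms. Here the preferred route is a counselor meeting, and such meetings are planned for different times in the two arms. Two things could follow.

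- **Selection and timing.** An Enhanced woman has a booked visit to which the survey can be attached. A Basic woman's survey depends more on her coming in for something else. If coming in is related to adherence, the Basic women who are surveyed need not represent their arm.
- **Reporting setting.** Table 2 shows that Enhanced counseling promotes daily use and addresses the beliefs that the attitude measures cover. A survey taken beside such a session may pick up immediate recall or a wish to please.

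The first could work against Enhanced and the second in its favor. Neither would be visible in the planned analysis. The Analysis Plan and the SAP name no missing-data method, and they compare self-report with blood results in the treatment group only, so over-reporting that differs by arm would not show.

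**Working it through.** **The plan's own figure.** Sampling gives 68 enrolled and 75% retained. 68 × 0.75 = 51, against the stated 50 (25 per arm), so the figure reproduces. It is one rate, not split by arm.

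**Planned counselor meetings at each assessment.** A month is taken as 30 days, and the Basic meetings as running to day 21.

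| Assessment | Enhanced | Basic | Gap since last planned Basic meeting |
|---|---|---|---|
| Month one (day 30) | monthly appointment | last planned meeting about day 21 | 30 − 21 = 9 days |
| Month three (day 90) | monthly appointment | on request only | 90 − 21 = 69 days |
| Month six | specialized counseling ended | on request only | no asymmetry created by planned meetings |

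If the Randomized Pilot text governs instead, Basic has no planned meeting at month one either. At month three both texts agree.

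**Which measures are exposed.** The in-person surveys are: self-reported adherence, self-efficacy, attitudes and decisional conflict. Blood or urine sampling is described with physician monitoring, and the doctor is not told the arm. The month-one texted adherence question needs no visit.

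**Is lost precision the problem?** With 34 randomized per arm and the plan's effect size of 0.79, approximate power is Φ(0.79/√(1/n₁ + 1/n₂) − 1.96). At 25 per arm this is Φ(2.793 − 1.960) = 0.798, which reproduces the stated 80%. Keep 75% retention overall but split it by arm (assumed splits, Enhanced/Basic):

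- 80%/70%: about 27 and 24 women, power 0.804
- 85%/65%: about 29 and 22 women, power 0.798
- 90%/60%: about 31 and 20 women, power 0.789

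Unequal numbers alone cost almost nothing. What matters is who is surveyed.

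**How large could selection be?** This is illustration only; every rate except the 75% is assumed. Let true adherence be p in both arms, let 75% of each arm be surveyed, and let being surveyed be unrelated to adherence in Enhanced. In Basic, a fraction a of adherent women is surveyed, and the rate among non-adherent women is (0.75 − p·a)/(1 − p). Observed Basic adherence is then p·a/0.75.

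- p = 0.20, a = 0.80: 0.16/0.75 = 21.3%, too high by 1.3 points
- p = 0.30, a = 0.85: 0.255/0.75 = 34.0%, too high by 4.0 points
- p = 0.50, a = 0.90: 0.45/0.75 = 60.0%, too high by 10.0 points
- p = 0.50, a = 0.70: 0.35/0.75 = 46.7%, too low by 3.3 points

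With the same p and a in both arms the difference is zero. Over-reporting in Enhanced would push the other way, and the documents give nothing from which to size it.

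**The case against.** The strongest reply is that the sentence states a convenience, not a rule. Staff only attempt it, a counselor meeting is only the ideal, and a visit for any other service also qualifies. Study staff contact both arms for every assessment; the bar on outreach applies to Basic counselors, not to the staff arranging surveys. Both arms have weekly medication pick-up at the site once PrEP is prescribed, many clients attend almost daily, and survey payments are the same in both arms. Nothing says the survey follows the counseling session; at baseline it comes first. All of this stands, and it turns the point into a risk rather than a documented difference.

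It does not remove the risk. Pick-up is open only to women prescribed PrEP and is itself close to adherence, so it is not a neutral fallback. Pick-up reminders are also weekly in Enhanced and bi-monthly in Basic.

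A reader might infer more than the documents support:

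- **That Basic data would come only from women who still attend or ask for counseling.** Staff outreach to both arms contradicts this.
- **That the whole primary outcome is compromised.** The drug-level measure is not affected by the counselor-meeting asymmetry, and neither is month six.
- **That payments widen the gap.** Compensation gives $10 per meeting "for meeting with the PrEP counselor (Up to four times"). If Basic women used all four by week three, a combined visit would pay Enhanced $10 + $10 = $20 against $10 at month one, and $20 + $10 = $30 against $20 at month three. That rests on a weekly reading of the Basic schedule, and the survey payment does not depend on counseling.
- **That no visit window exists.** The available text gives only nominal times, but the timeline attachment it cites was not available.

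**Conclusion.** The preference for counselor meetings, set against arm-specific counseling schedules, can make the timing, setting and completeness of the in-person surveys differ by arm. The gap is clear at month three and small at month one, about nine days if Basic meetings run to week three. Enhanced self-report may also be taken next to a session promoting adherence.

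The documents do not fix the size or direction of any bias. The 1 to 10 point range for overstated Basic adherence depends on assumed rates (true adherence 20% to 50%, and 80% to 90% of adherent Basic women surveyed), with selection acting in Basic only. Power is barely affected. The sponsor should make the change: in a pilot meant to give directional insight, an avoidable bias of unknown sign in self-reported adherence and attitudes is worth removing. The trial does not stand or fall on it.

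**What to change.** In Procedure Phase 3:

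1. Delete the preference for counselor meetings as the occasion for assessment.
2. Have research staff arrange the assessments, counted from randomization, with the same window and the same number of contact attempts in both arms. The sponsor chooses the width. Any convenient on-site visit within the window remains acceptable; banning opportunistic assessment could cost retention in this population.
3. If a counseling session falls on the same day, complete the survey before it.
4. Report assessment date, setting and completion by arm, and add this to the SAP.

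The counseling passages should also be reconciled: on-request control counseling, Basic meetings through week three, at least four meetings expected without regard to arm, and counselor follow-up of missed pick-ups without regard to arm although Basic counselors do not reach out.

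The cost is protocol wording, calendar entries in REDCap and some scheduling effort. Staff already contact every participant. Some Enhanced women will take the survey before counseling. The counseling, materials and text messages stay as planned in both arms.

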statistic if the data is non-normally distributed) and chi-square test for categorical measures (or Fisher's Exact test if appropriate). Blood test results will also be compared to adherence benchmarks for Tenofovir-Emtricitabine and categorized as a binary variable (yes/no) based upon the mean value observed by all patients, with data at one month, three months and three months post intervention. We will use ANCOVA to assess differences between self-reported adherence and adherence as measured by blood test in the treatment group. Primary efficacy analyses will be a comparison of experimental to control group at one month, three months and three months post intervention, while other subgroup analyses based on race/ethnicity or age, for instance, as well as potential mediators and moderators, will be considered post-hoc exploratory analyses. In addition, logistic regression modeling will be used for binary adherence measures to assess group differences. Model assumptions will be tested, including linearity between the logit of the independent variables and the dependent, multicollinearity, and model misspecification.

Secondary outcomes. Secondary outcomes include self-efficacy, PrEP attitudes and decisional conflict. These measures are all continuous. Following evaluation of the primary outcome, we will explicitly examine the association between treatment adherence characteristics and extent of change among individuals in the treatment conditions in order to evaluate dose-response associations. Multiple linear models will be used to examine relationships between the groups and decisional conflict scale items, self-efficacy, and PrEP attitude scales at month three and three months post intervention. In these models, baseline outcome measures will be adjusted as covariate in the model development. PrEP attitudes will also be assessed through perceptual mapping analysis and compared from baseline to three month and three month follow-up for each group to assess "movement" toward adherence and away from negative perceptions of PrEP use. Promise of efficacy would indicate more movement by those in the "Enhanced" group compared to the "Basic" group. We will also explore potential mediators and moderators (HIV stigma, depression, level of drug use, social support). Outliers will be assessed using standardized residuals; if necessary, analyses will be accomplished for all data as well for non-outlying cases only.

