Acceptability and feasibility will be analyzed using survey items and objective measures (opened text messages, prescription pick-up). Quantitatively we will assess each feasibility and acceptability measure in both groups by inspecting trajectory plot of mean levels of satisfaction over time. No formal testing is proposed except for the descriptive statistics summarized at each follow-up assessment. We will also explore associations between participant characteristics and acceptability in order to identify subgroups of participants for whom the intervention may be less acceptable. Qualitative data will be collected via open-ended answers on the mid-intervention, post intervention and three month follow-up survey. This data will be analyzed using the Krueger method of analyzing narrative data. A thematic framework will be developed to create categories and quotes will be indexed according to categories to reduce data. Charting of quotes to enable analysis will then occur. These quotes, along with items with low mean ratings and those with the highest proportion of disagree and strongly disagree responses, will be used to assess acceptability and feasibility to inform development of a full-scale intervention.

Power calculations are not provided because we will be pilot testing a new intervention, and its effect size is not known. We have not fully powered the randomized test due to the study's size and purpose, which is to assess the feasibility, acceptability and promise of efficacy of the intervention, however with a projected n=25 in each group comparing adherence we have 80% power to detect an effect size of 0.79 (if it is a continuous measure) or an OR or 2.56 (if binary). Positive results will aid in our ability to further test the intervention in a fully powered randomized controlled trial and whether it is feasible in the context of offering it in a community-based, clinical setting.

Procedures Involved in Human Research

Description of Protocol

Consent Process

HRP-802=-Investigator Guidance Informed Consent will be followed to obtain informed consent. Before all assessments, a research staff member will review the written informed consent with the participants. Participants will have time to review the material and will be reminded that their participation is voluntary.

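### The plan does not say whether biomedical adherence is decided on the drug level or on a yes/no split of it, and the two forms can give different answers

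*Combined protocol and SAP*

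**What the plan says.** The protocol's Analysis Plan and the SAP carry the same text on this point.

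- **Menu of tests (Primary Outcome).** "univariate group comparisons will be accomplished using an independent two-sample t-test for continuous measures", with Wilcoxon if the data are non-normal, and chi-square or Fisher for categorical measures.
- **Blood results (Primary Outcome).** "Blood test results will also be compared to adherence benchmarks for Tenofovir-Emtricitabine and categorized as a binary variable (yes/no"), with the split placed at the mean of all patients.
- **Second test of the binary form (Primary Outcome).** "In addition, logistic regression modeling will be used for binary adherence measures to assess group differences".
- **Significance rule (General).** "tests for differences in means and proportions will be deemed statistically significant $p < 0.05". The only adjustment covers other tests: "Post-hoc tests of significance will be based on adjustments for alpha to protect family-wise error rates at 5" per cent.
- **Power paragraph.** "we have 80% power to detect an effect size of 0.79 (if it is a continuous measure"), or an OR of 2.56 if it is binary. The form is left open.

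Three other places bear on the point. The Randomized Pilot text and the Procedure section allow either blood or urine for the biomedical measure. The Privacy section gives adherence as an example of data entered in REDCap as 0 or 1. Attachment I (outcomes and source) is listed but was not available.

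**The concern.** The primary efficacy comparison is Enhanced against Basic at each visit, but the form of the biomedical measure in that comparison is not named. If the level is compared as a continuous value and then also as yes/no, one assay at one visit yields up to three p-values: t-test or Wilcoxon, chi-square or Fisher, and logistic regression. All answer the same question at the same threshold.

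Positive results are meant to support a full-scale trial, so a reader needs to know which result counts. Choosing a lead visit, choosing between biomedical and self-reported adherence, or changing the cut-off would not settle this, because the two forms sit within one visit and one assay. The forms also differ in power, and the single 80% statement covers both.

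**Working it through.** **Inputs.** From the power paragraph: 25 per arm, 80% power, 0.79 SD, OR 2.56. From General: p<0.05 per test. From Primary Outcome: split at the mean of all patients. Assumed: two-sided tests (sidedness is not stated, but "All parameter estimates will be bound by 95% confidence intervals" and step 1 point that way) and normal levels with equal SD, with log-normal levels as the alternative.

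**1. The plan's continuous figure.** Detectable effect = (1.960 + 0.842) × √(2/25) = 2.802 × 0.2828 = 0.792. Power at 0.79 = Φ(0.79 × √(25/2) − 1.960) = Φ(2.793 − 1.960) = Φ(0.833) = 79.8%, or 78.1% with the noncentral t. The stated 80% reproduces. A one-sided test would give about 87%.

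**2. The plan's binary figure.** With control rate p1, p2 = OR·p1 / (1 − p1 + OR·p1). Power = Φ{[(p2 − p1) − 1.960·√(2p̄(1 − p̄)/n)] / √([p1(1 − p1) + p2(1 − p2)]/n)}, where p̄ is the mean of p1 and p2. For p1 = 0.40, p2 = 1.024/1.624 = 0.6305 and p̄ = 0.5153. Power = Φ[(0.2305 − 0.2771)/0.1375] = Φ(−0.34), about 37%. Control rates from 10% to 70% give 21% to 37%. Reaching 80% needs an OR of at least about 5.1. The binary figure does not reproduce.

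**3. Do the two forms agree at the plan's effect?** Simulated trials, 25 per arm, pooled-mean split, 100,000 per setting (20,000 for Wilcoxon). The log-normal setting has a shift of 0.79 on the log scale.

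| Result at 0.79 SD | Normal | Log-normal |
|---|---|---|
| t-test significant | 78.3% | 59.1% |
| Wilcoxon significant | 75.5% | 75.0% |
| Chi-square significant | 64.9% | 55.7% |
| Fisher significant | 53.6% | 41.3% |
| Logistic (Wald) significant | 55.2% | 52.7% |
| t-test and chi-square disagree | 20.2% | 23.6% |
| of which t-test only / chi-square only | 16.8% / 3.4% | 13.5% / 10.1% |
| t-test and Fisher disagree | 27.9% | 28.2% |
| Wilcoxon and chi-square disagree | 17.2% | 25.8% |

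With a fixed cut-off that 20% to 70% of controls exceed, and normal levels, the t-test and chi-square disagree in 21% to 35% of trials.

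**4. No true effect, same design.**

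| Result under no effect | Normal | Log-normal |
|---|---|---|
| t-test alone | 4.9% | 4.1% |
| Chi-square alone | 6.7% | 5.3% |
| t-test or chi-square | 4.9 + 4.1 = 9.0% | 4.1 + 3.3 = 7.4% |
| t-test or Fisher | about 6.5% | about 5% |

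For normal levels, having two forms adds 9.0 − 6.7 = 2.3 points to what chi-square does alone.

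**5. With one form named.** Normal levels, 0.79 SD: power is 78% if the level decides (t-test), against 65% (chi-square), 55% (logistic) or 54% (Fisher) if the split decides.

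**The case against.** **The t-test on the level is inferred.** No sentence says that the drug level itself is t-tested. The tests form a generic menu, the only form spelled out for blood results is yes/no, and the Privacy section codes adherence 0/1. A reader might infer that double testing is written into the plan; the documents do not go that far. What stands is the ambiguity. The word "also" in the blood-results sentence implies another form, and a split at the mean of all patients cannot be made without the numeric levels. If only yes/no was meant, the plan still does not say so, and the 0.79 figure would not apply to it.

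**The null inflation is modest and depends on the test.** A reader might infer that two forms nearly double the false-positive rate. Part of the 9% is chi-square's own excess size, and with Fisher the figure is about 6.5% or 5%.

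**The disagreement is mainly lost power.** For normal levels the split rescues a failed t-test in only about 3% of trials. This is correct, and the 20% should not be read as the chance of a spurious claim. Nor do the documents suggest that only the favourable result would be reported.

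**It is a pilot.** The plan says it seeks direction for later studies, is not fully powered, and sets no p-value as a gate to the next trial. This lowers the priority but leaves open which result counts as positive.

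**Preferring the continuous form is a judgement.** The power paragraph gives each form its own figure, and blood and urine may not share a scale. The text itself supports only the request to name one form; the preference is conditional.

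**Conclusion.** The concern holds as a gap in specification. The available text can be followed to more than one verdict on biomedical adherence at a visit, and nothing in it ranks them. Attachment I could, but was not available.

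With 25 per arm, two-sided 5%, normal levels, a pooled-mean split and chi-square, the two forms disagree in about 20% of trials at 0.79 SD: about 17% t-test only and 3% split only. With Fisher the rate is about 27-28%. One in five is therefore conditional, and other tests, cut-offs and distributions move it. Under no effect, the chance that either form is significant is about 9% (normal) or 7% (log-normal) with chi-square, and about 6.5% or 5% with Fisher.

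The 80% power statement is right for the continuous form and wrong for OR 2.56, which gives about 21-37%. The power advantage of the level is clear for normal data. For log-normal data it depends on using the Wilcoxon test, which the plan already provides for (75% against 59% for the t-test).

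**What to change.** 1. **Primary Outcome, protocol and SAP.** Name one form as the deciding analysis of biomedical adherence. The continuous level is preferable to a split at the sample mean, because it keeps more power and the stated 80% at 0.79 reproduces only for it. This holds only if one specimen type on a common scale is used and the numeric level is recorded. Suggested sentence: *The between-arm comparison of the numeric drug level is the deciding analysis of biomedical adherence; the yes/no proportions are supportive and descriptive.*
2. **The other form.** Report it by arm with a difference and 95% interval from one stated method. Drop the duplicate test of the yes/no variable (chi-square/Fisher or logistic regression).
3. **Reconcile** this choice with the blood-or-urine wording in the Randomized Pilot and Procedure sections, and with the 0/1 coding in the Privacy section. If a common numeric scale cannot be had, name the yes/no form and one test for it instead.
4. **Power paragraph, protocol and SAP.** Limit the 80% statement to the continuous form and remove or correct the OR of 2.56.
5. **Attachment I.** Check that it agrees.

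The cost is more than wording: the numeric level must be captured and the specimen settled. The yes/no proportion, which is easier to explain clinically, would no longer support a significance claim, though it is still reported. Given the pilot purpose, the priority is modest.
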